3.3.5 Procedures for discontinuation

If study treatment is prematurely discontinued prior to the 12 weeks of treatment, patients will be asked to come in for a study termination visit, and the procedures and assessments as described for week 12 in section 3.2 “Study Plan” will be performed.

3.3.6 Replacement Policy

Patients who do not initiate study assigned therapy after signing consent or do not complete the week 4 blood draw for safety evaluation will be considered unevaluable and will be replaced.

4. TREATMENTS

4.1 ESTRING

ESTRING (estradiol vaginal ring) is a slightly opaque ring with a whitish core containing a drug reservoir of 2 mg estradiol. Estradiol, silicone polymers and barium sulfate are combined to form the ring. ESTRING has the following dimensions: outer diameter 55 mm; cross-sectional diameter 9 mm; core diameter 2 mm. When placed in the vagina, ESTRING releases estradiol, approximately 7.5 µg/24 hours, in a consistent stable manner over 90 days. Estradiol is chemically described as estra-1,3,5(10)-triene-3,17β-diol. The molecular formula of estradiol is C₁₈H₂₄O₂, and the molecular weight of estradiol is 272.39.

One ESTRING should be inserted into the upper third of the vaginal vault, to be worn continuously for three months.

4.1.1 Pharmacokinetics

Absorption

Estrogens used in therapeutics are well absorbed through the skin, mucous membranes, and the gastrointestinal (GI) tract. The vaginal delivery of estrogens circumvents first-pass metabolism possibly reducing the induction of several other hepatic proteins. In a Phase I study of 14 postmenopausal women, the insertion of ESTRING (estradiol vaginal ring) rapidly increased serum estradiol (E₂) levels attesting to the rapid absorption of estradiol via the vaginal mucosa. The time to attain peak serum estradiol levels (T_{max}) was 0.5 to 1 hour. Peak serum estradiol concentrations post-initial burst declined rapidly over the next 24 hours and were virtually indistinguishable from the baseline mean (range: 5 to 22 pg/mL). Serum levels of estradiol and estrone (E₁) over the following 12 weeks during which the ring was maintained in the vaginal vault remained relatively unchanged (See Table 1.) The initial estradiol peak post-application of the second ring in the same women resulted in ~38% lower C_{max}, apparently due to reduced systemic absorption via the revitalized vaginal epithelium. The relative systemic exposure from the initial peak of ESTRING accounted for approximately 4% of the total estradiol exposure over the 12 week period.

TABLE 1: PHARMACOKINETIC MEAN ESTIMATES FOLLOWING ESTRING APPLICATION

Estrogen	C _{max} (pg/mL)	C _{ss-48 hr} (pg/mL)	C _{ss-4w} (pg/mL)	C _{ss-12w} (pg/mL)
Estradiol (E ₂)	63.2 ^a	11.2	9.5	8.0
Baseline-adjusted E ₂	55.6	3.6	2.0	0.4
Estrone (E ₁)	66.3	52.5	43.8	47.0
Baseline-adjusted E ₁	20.0	6.2	-2.4	0.8

^a n=14

The constant and stable release of estradiol from ESTRING was demonstrated in a Phase II study of 166 - 222 post-menopausal women who inserted up to four rings consecutively at three month intervals. Low dose systemic delivery of estradiol from ESTRING resulted in mean steady state serum estradiol estimates of 7.8, 7.0, 7.0, 8.1 pg/mL at weeks 12, 24, 36, and 48, respectively. Similar reproducibility is also seen in levels of estrone. Lower systemic exposure to estradiol and estrone is further supported by serum levels measured during a pivotal Phase III study. In post-menopausal women, mean dose of estradiol systemically absorbed unchanged from ESTRING is ~ 8% [95% CI: 2.8-12.8%] of the daily amount released locally.

4.1.2 Pharmacodynamics

In-vivo, estrogens diffuse through cell membranes, distribute throughout the cell, bind to and activate the estrogen receptors, thereby eliciting their biological effects. Estrogen receptors have been identified in tissues of the reproductive tract, breast, pituitary, hypothalamus, liver and bone of women. ESTRING delivers estradiol constantly at a mean rate of ~7.5 µg/24 hours for a period of up to 90 days. Its use in post-menopausal patients in Phase I and II studies showed no apparent effects on systemic levels of hepatic protein SHBG, or FSH. Lowering of the pretreatment vaginal pH from a mean of 6.0 to a mean of 4.6 (as found in fertile women) over the 12 to 48 week treatment period, and improvements evident in the vaginal mucosal epithelium seen in all studies attest to the local dynamic effects of estrogens.

4.1.3 Special Populations

- **Postmenopausal Women** - Estrogens have been reported to increase the risk of endometrial carcinoma in post menopausal women. Adequate diagnostic measures, including endometrial sampling when indicated, should be undertaken to rule out malignancy in all cases of undiagnosed persistent or recurring abnormal vaginal bleeding.
- **Pregnancy** - There is no indication for estrogen therapy during pregnancy or during immediate postpartum period. Estrogen therapy during pregnancy is associated with an increased risk of congenital defects in the reproductive organs of the fetus, and possibly other birth defects. Studies of women who received diethylstilbestrol (DES) during pregnancy have shown that female offspring have an increased risk of vaginal adenosis, squamous cell dysplasia of the uterine cervix, and clear cell vaginal cancer later in life; male offspring have an increased risk of urogenital abnormalities and possibly testicular cancer later in life. The 1985 DES Task Force concluded that the use of DES during pregnancy is associated with a subsequent increased risk of breast cancer in the mothers, although a causal relationship remains unproven and the observed level of excess risk is similar to that for a number of other breast cancer risk factors.
- **Breast cancer** - While the majority of studies have not shown an increased risk of breast cancer in women who have ever used estrogen replacement therapy, some have reported a moderately increased risk (relative risks of 1.3 to 2.0) in those taking higher doses or those taking lower doses for prolonged periods of time, especially in excess of ten years. The package for ESTRING states that estrogens

in general are contraindicated in women with a known or suspected carcinoma of the breast or other types of estrogen dependent malignancies.

4.1.4 Geriatric Use

Of the total number of subjects in clinical studies of ESTRING (including subjects treated with ESTRING, placebo, and comparator drug; n=951), 25% were 65 and over, while 4% were 75 and over. No overall differences in safety or effectiveness were observed between these subjects and younger subjects, and other reported clinical experience has not identified differences in responses between the elderly and younger patients, but greater sensitivity of some older individuals cannot be ruled out.

4.1.5 Drug-Drug Interactions

Drug-drug and drug-laboratory interactions have been reported with estrogen administration overall, but were not observed in clinical trials with ESTRING. However, the possibility of the following interactions should be considered when treating patients with ESTRING:

1. Accelerated prothrombin time, partial thromboplastin time, and platelet aggregation time; increased platelet count; increased factors II, VII antigen, VIII antigen, VIII coagulant activity, IX, X, XII, VII-X complex, II-VII-X complex, and betathromboglobulin; decreased levels of anti-factor Xa and antithrombin III, decreased antithrombin III activity; increased levels of fibrinogen and fibrinogen activity; increased plasminogen antigen and activity.
2. Increased plasma HDL and HDL-2 subfraction concentrations, reduced LDL cholesterol concentration, increased triglycerides levels.

4.1.6 How Supplied

Each ESTRING (estradiol vaginal ring) is individually packaged in a heat-sealed rectangular pouch consisting of three layers, from outside to inside: polyester, aluminum foil, and low density polyethylene, respectively.

NDC 0013-2150-36 ESTRING (estradiol vaginal ring) 2 mg - available in single packs.

4.1.7 Storage

ESTRING should be stored at controlled room temperature 15° to 30° C (59° to 86° F) per recommendation of the package insert.

4.2 Testosterone cream 1% micronized in velvachol

There are a number of different esters of testosterone, including the commonly prescribed injectables of testosterone enanthate and testosterone cypionate, as well other esters such as acetate, propionate, phenylpropionate, isocaproate, caproate, decanoate, and undecanoate. Esterification of testosterone is done in order to improve the solubility of testosterone in oil,

which in turn slows the release of the testosterone from the site at which it enters the body. A number of formulations of androgen replacement have been tested in men, including injections, oral supplementation (either testosterone undecanoate, methyltestosterone, oxandrolone, or DHEA), transdermal testosterone patches, testosterone creams or gels, and subcutaneous testosterone implants. Based on a number of studies, the transdermal route (either patch, cream, or gel) appears to have the most favorable pharmacokinetic properties of available testosterone preparations tested in women.

TESTOSTERONE, MICRONIZED, USP (T1006)

Synonyms: 4-Androsten-17beta-ol-3-one; 17beta-Hydroxy-4-androsten-3-one
(C₁₉H₂₈O₂ : F.W. 288.42)

Testosterone cream will be produced by the UCSF Drug Product Services. The pharmacy has provided us with details of the preparation of the testosterone cream as follows:

The appropriate amount of pure testosterone chemical is weighed to produce a 1% concentration. The powder is levigated with mineral oil, and then this mixture is brought to the desired volume with velvachol.

Velvachol is a water-miscible compounding vehicle in a non-sticky, non-greasy, odorless base that is compatible with a wide variety of chemicals used in topical therapy. Velvachol is stable and neutral in reaction, and washes easily from the hair, skin and clothes. It is physically compatible with acids, bases, strong electrolytes and many other medications commonly applied to the skin. Velvachol is formulated in a hydro-philic emulsion-type base.

4.2.1 Testosterone Cream Absorption and Pharmacokinetics

Extrapolating from the fact that systemic absorption of estrogens is robust after the topical administration of estrogen creams vaginally, absorption of testosterone cream through the vaginal mucosa would be expected to be significant as well, but the pharmacokinetics have not been well described.

4.2.2 Testosterone Cream Storage

The product is dispensed in a plastic opaque tube with an applicator for vaginal administration. The product is stored at room temperature. The expected shelf life is 6 months.

4.3 Doses and treatment regimens

- Testosterone Cream 1% micronized in velvachol - 0.5 gm of cream vaginally 3 times a week for total of 12 weeks of treatment
- ESTRING 2mg ring inserted vaginally once every 12 weeks

4.4 Mechanism of drug storage and destruction

Study drugs will be obtained as a special order from the UCSF Pharmacy (in the case of the ESTRING) or from the UCSF Drug Product Services Laboratory (in the case of the testosterone cream). Due to the limited shelf life of testosterone cream, this will be prepared in

batches of a 10 patient supply. Both the ESTRING and the testosterone cream will be stored under appropriate conditions and dispensed by the investigational pharmacist at the UCSF Mt. Zion Infusion Center Pharmacy. When patients have completed their 12 weeks of study treatment, they will be advised to remove and discard the ESTRING. For patients on the testosterone cream arm, patients will be advised to discard any remaining study drug, or if they choose, to continue using the remaining cream until it gone. Therefore, documentation indicating study drug was destroyed is not applicable to this study.

4.5 Pre-study, concomitant and post-study treatment(s)

Use of vaginal hormonal products (rings, inserts, creams, gels) containing estrogens or androgens within the past 90 days is not permitted.

Treatment with any type of oral, injectable or topical form of estrogen or androgen therapy including natural supplements marketed as hormone replacement products is not permitted during the 12 weeks of study treatment. Initiation or change in usage pattern of moisturizing agent, herbal or alternative medicine to manage the symptoms of vaginal dryness is not permitted during the 12 weeks of treatment.

There are no limitations on post-study treatments.

5. SAFETY MEASUREMENTS AND VARIABLES

5.1 Adverse events

5.1.1 Definitions

Adverse event

An adverse event is the development of an undesirable medical condition or the deterioration of a pre-existing medical condition following or during exposure to a pharmaceutical product, whether or not considered causally related to the product. An undesirable medical condition can be symptoms (*e.g.*, nausea, chest pain), signs (*e.g.*, tachycardia, enlarged liver) or the abnormal results of an investigation (*e.g.*, laboratory findings, electrocardiogram). In clinical studies, an AE can include an undesirable medical condition occurring at any time, including run-in or washout periods, even if no study treatment has been administered.

Serious adverse event

A serious adverse event is an AE occurring during any study phase (*e.g.*, run-in, treatment, washout, follow-up), and at any dose of the investigational product, comparator or placebo, that fulfils one or more of the following criteria:

- results in death
- is immediately life-threatening
- requires in-patient hospitalization or prolongation of existing hospitalization

- results in persistent or significant disability or incapacity
- is a congenital abnormality or birth defect
- is an important medical event that may jeopardize the subject or may require medical intervention to prevent one of the outcomes listed above.

The causality of SAEs (their relationship to study treatment) will be assessed by the investigator(s).

5.1.2 Recording of adverse events

Adverse events will be recorded at week 4 and at the end of the study (week 12 visit). For each AE, the onset, intensity, action taken, and resolution will be recorded. Efforts will be made to assign causality. All events will be evaluated to determine if they represent a SAE. Adverse events will be graded according to the NCI Common Terminology Criteria for Adverse Events (CTCAE) version 3.0.

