The primary outcome variable in this study is the number of breast cancer patients being treated with either intravaginal testosterone cream or the ESTRING for a 12 week period who are found to have a persistently elevated serum estradiol level outside the post-menopausal range as defined by:

1. An elevation of serum estradiol outside of the post-menopausal range and at least 10 pg/ml higher than the baseline value on two consecutive collections at least four weeks apart.
The post-menopausal range at UCSF is ≤ 10 pg/ml (as measured by Quest Diagnostics, the lab utilized by the UCSF clinical laboratory).

2. If a patient's baseline (day 1) serum estradiol level is >10 pg/ml, the subsequent levels must be >10 pg/ml higher than the baseline value to be considered a significant elevation outside the post-menopausal range.

A secondary outcome variable is the change in scores on the CARES Sexual Dysfunction Subscale from baseline to week 12. The ESTRING and testosterone cream treatment groups will be analyzed independently.

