3.2 Study plan

Visit	Screening/Baseline	Week 4 ^{a,b}	Week 8-10 ^c	Week 12 ^a	Week 16-18 ^c	Early Withdrawal
Day	-28 to 1	23-33		79-89		
Sign Informed Consent	X					
Medical History	X					
Inclusion /exclusion criteria	X					
Gynecologic Exam ^d	X			X ^e		X
Physical Exam ^f	X					
ECOG status	X					
Concurrent Medication	X			X		X
Chemistry/Hematology ^g	X					
Serum Hormone Measurements ^h	X	X	X	X	X	X
Completion of QOL questionnaires	X	X		X		X
Dispense study medication	X ⁱ					
Adverse Events		X		X		X

- a. May occur \pm 5 days from day 28 (week 4) or day 84 (week 12).
- b. Clinic visit is optional.
- c. Visit is only for patients with abnormal estradiol levels at week 4 or week 12. Test does not include testosterone levels. [If the week 4 or week 12 estradiol level is outside the postmenopausal range (or if there is a >10 pg/ml increase in estradiol levels in patients with an estradiol level above the post-menopausal range at baseline), a repeat sample will be sent within 4-6 weeks. Therefore, estradiol will be repeated by week 10 for a patient with an elevation at week 4, and by week 18 for a patient with an elevation at week 12.]
- d. The physician's assessment of the vaginal epithelium will include a 3-point scale to evaluate color, petechiae, friability and dryness.
- e. Performed sooner if patient drops out or experiences unexpected side effects
- f. Limited exam consisting of cardiac and lung auscultation and abdominal exam only
- g. Includes CBC with differential, AST, alkaline phosphatase, total bilirubin. Abnormal results will be followed up at the investigator's discretion as per standard of care.
- h. Includes estradiol levels for all patients and serum testosterone levels only for patients randomized to the testosterone cream arm.
- i. Must be done on Day 1.

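### The week 16-18 estradiol redraw can decide a primary-endpoint failure, but outside hormones are allowed by then and no medication or adverse event entry is scheduled

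*Protocol*

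**What the plan says.** - **Endpoint (3.1).** A woman fails if her estradiol is above 10 pg/ml and at least 10 pg/ml over baseline "on two consecutive collections at least four weeks apart".
- **Redraw (3.2, footnote c).** After a raised week-4 or week-12 value, "a repeat sample will be sent within 4-6 weeks", which means "by week 18 for a patient with an elevation at week 12".
- **Schedule (3.2 table).** The week 16-18 column marks only the hormone draw. Concurrent Medication is marked at baseline, week 12 and early withdrawal. Adverse Events is marked at week 4, week 12 and early withdrawal. Section 5.1.2 agrees with the table and treats week 12 as the end of the study: "Adverse events will be recorded at week 4 and at the end of the study (week 12 visit".
- **Leftover product (4.4).** On the cream arm, "patients will be advised to discard any remaining study drug, or if they choose, to continue using the remaining cream until it gone". Women on the ESTRING are told to take the ring out and throw it away.
- **Other hormones (4.5).** Outside estrogen and androgen are barred for the 12 treatment weeks. After that, "There are no limitations on post-study treatments".

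**The concern.** The primary endpoint can be completed 4 to 6 weeks after treatment ends, but hormone exposure is neither controlled nor recorded in that interval. If the confirming value is high, the woman counts as a failure. No scheduled entry shows whether she was using leftover cream, had started another estrogen or androgen, or had stopped her aromatase inhibitor or GnRH agonist. The report then cannot say whether the value reflects the 12-week treatment.

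The possibility is realistic. Section 1.2 describes the clinic's practice of moving to the alternate treatment when relief is insufficient, and to the Vagifem insert in severe cases. Section 3.3.2 admits women whose amenorrhea depends on a GnRH agonist.

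A smaller matter is that new non-serious events, such as bleeding or irritation, have no scheduled capture in women who are still being seen because their estradiol is raised.

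**Working it through.** **1. Which women depend on the late draw.** A raised week-4 value is repeated by week 10, so a failure that begins at week 4 can be confirmed on treatment. For a first elevation at week 12, the only later collection is the one at week 16-18. Footnote c brings back any woman outside the postmenopausal range, whereas failure also needs the 10 pg/ml rise over baseline. Not every woman who returns is therefore a candidate failure.

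**2. When the draw falls.** The week-12 window is day 79-89 (3.2).
- Earliest: 79 + 28 = day 107.
- Latest: week 18 = 18 × 7 = day 126. Adding 42 days to day 89 gives 131, but footnote c stops at week 18.
- From a nominal day 84: 84 + 28 = 112 to 84 + 42 = 126.

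The stretch without a scheduled medication or adverse event entry is thus 28 to 42 days.

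**3. Could leftover cream last that long?** The course is 0.5 g × 3 × 12 = 18 g (4.3). Dosing at the trial rate up to the redraw would need 0.5 × 3 × 4 = 6 g to 0.5 × 3 × 6 = 9 g, or 33% to 50% of a course. The amount dispensed is not stated, so how many women could still be dosing is unknown.

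**4. Could another hormone produce a qualifying value?** Section 1.1 reports seven women on aromatase inhibitors using Vagifem. Their estradiol rose from 5 pmol/l or less to a mean of 72 pmol/l at 2 weeks. With the molecular weight of 272.39 in 4.1, 72 × 0.27239 = 19.6 pg/ml and 5 × 0.27239 = 1.4 pg/ml, a rise of about 18 pg/ml. That would meet both thresholds. By 4 weeks the median was 16 pmol/l (16 × 0.27239 = 4.4 pg/ml), which would not. The assay there was a special low-level one, so this shows possibility only.

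**5. The plan's own operating figures.** The rule is 10 + 25 women per arm, closing at 3 or more failures in the first 10 and declaring the arm unsafe at 5 or more of 35 (7.2). The probability of a safe verdict is

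P(safe) = Σ over x = 0 to 2 of P[Bin(10, p) = x] × P[Bin(25, p) ≤ 4 − x].

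| True failure rate | Stated | Recomputed |
|---|---|---|
| 5% | 98% | 96.4% |
| 10% | 70% | 71.4% |
| 25% | 5% | 3.9% |

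The recomputed values are within 2 points of those stated, and this point does not dispute them.

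**6. Size and direction.** Expected failures per arm by any route are 35 × 0.05 = 1.75 and 35 × 0.10 = 3.5. Only some would be confirmed at week 16-18, and that share is not given. One woman is 1/35 = 2.9 points, and the verdict turns between 4/35 (11.4%) and 5/35 (14.3%).

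Unrecorded hormone use can turn a non-failure into a failure, but not the reverse. The null hypothesis is that the treatment is unsafe, so extra failures keep the null. As an illustration with assumed shifts that are not in the documents, suppose contamination raised the failure rate:
- from 5% to 7.5%: P(safe) falls from 96.4% to 86.8%;
- from 10% to 12.5%: from 71.4% to 53.6%;
- from 10% to 15%: from 71.4% to 36.8%.

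The last is an extreme case. Five points is 1.75 women per arm, as many as all the failures expected at the 5% planning rate.

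**The case against.** The strongest reply is that recording changes no result. A woman noted as using leftover cream still counts as a failure under 3.1, and five failures still make the arm unsafe. This stands. The medication entry makes a failure interpretable but does not remove it. Only an extended ban on outside hormones reduces contamination, which is why that ban belongs in the main fix.

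Second, the size is unknown, and the 4-versus-5 boundary applies to any single patient. This also stands: the boundary says what one woman is worth, not how many women are affected.

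Third, scheduled adverse event questions at week 16-18 would give a longer observation period only to women with raised estradiol, so these events cannot be pooled with the 12-week comparison. This stands too, and makes the adverse event part secondary.

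Fourth, existing text gives some cover. The synopsis promises monitoring throughout the study, 5.1.1 includes washout in the adverse event definition, 5.1.2 records the resolution of each event, and 7.6 sets weekly review. None of this schedules questions to a patient after week 12, and none of it concerns medication. The reply narrows the point without closing it.

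**Conclusion.** The point holds as a minor one. For a woman whose first raised estradiol is at week 12, a raised confirming value cannot be attributed to the 12-week treatment, because exposure after week 12 is neither restricted nor recorded. Few women are affected, and the number cannot be derived from the protocol. Leftover product concerns the cream arm only; outside hormones concern both arms.

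Three stronger readings are tempting but not supported:
- **That an unsafe treatment could pass as safe.** Contamination adds failures, so it costs power and does not raise the chance of a false safe verdict.
- **That a repeat testosterone level would reveal leftover cream use.** Footnote c does omit that test, but 4.2.1 says the cream's pharmacokinetics are poorly described. The documents do not establish testosterone as a marker of recent use.
- **That serious events go unreported after week 12.** The definition in 5.1.1 covers washout and follow-up, and 5.1.3 sets no end date for reporting unexpected, possibly drug-related serious events.

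The conclusion rests on reading the blank week 16-18 cells as intended, which 5.1.2 supports for adverse events.

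**What to change.** **Main change**
- In the 3.2 table, mark Concurrent Medication at week 16-18. Ask about leftover study cream, any other estrogen or androgen, and aromatase inhibitor or GnRH agonist use since week 12.
- In 4.5, for women with a raised week-12 estradiol, extend the ban on estrogen and androgen to the repeat draw. Word it as covering hormones other than remaining study cream, so that it does not contradict 4.4. The ban can take effect only once the week-12 result is known, and the medication question picks up anything started before then.

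**Secondary change**
- Mark Adverse Events at week 16-18 and amend 5.1.2 to name that visit where it occurs. Report these events separately from the 12-week comparison, since only women with raised estradiol return.

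The counting rule, sample size and decision boundaries stay as they are. The cost is a wording amendment, a few minutes of questions at a visit that already takes place, and a wait of 4 to 6 weeks before another hormone for the women concerned.
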